7.4. Short IQCODE questionnaire for dementia

The short version of the 'Informant Questionnaire on Cognitive Decline in the Elderly' (IQCODE) is a validated screening tool which measures cognitive decline and is completed by an 'informant' (usually a relative or friend) nominated by the participant.^{13,14}

The short IQCODE questionnaire has been widely used in previous postal and telephone studies of cognition and dementia and has been found to be acceptable to participants and informants and therefore we do not expect any significant risks associated with it.

7.5. Randomisation, blinding and code-breaking

There will be no randomisation in use during this long-term follow-up study of ACST-1 participants.

During the enrolment period of ACST-1 (1993-2003), randomisation was through the Clinical Trial Service Unit (CTSU; Oxford, UK) where patients were allocated equally to immediate CEA or deferral of any carotid surgery.

All data processing and analysis relating to outcome ascertainment for this follow-up study will be performed blind to the allocated group.

8. INTERVENTIONS

No further interventions are planned as part of this study.

In ACST-1 CEA was to be done as soon as routinely possible. Surgeons' normal operative techniques were used; shunting during surgery to maintain perfusion was optional, and anaesthetic technique was decided locally. Participants allocated to deferral were not to be treated unless they later developed carotid territory symptoms or some other indication for surgery (or unless the doctor or participant changed their mind). Both groups were to receive appropriate medical care.

9. STATISTICS AND ANALYSIS

9.1. The Number of Participants

Between 1993 and 2003, the ACST-1 trial included 3120 participants from 30 countries (n=1601 from UK and Sweden). Asymptomatic patients with substantial carotid stenosis, considered suitable for surgery were randomly allocated to a policy of immediate carotid endarterectomy plus contemporary medical management versus contemporary medical management alone. Of those allocated immediate endarterectomy, 90% had the procedure within 1 year after randomisation (92% by 10 years); of those

allocated to deferral, 7.5% had the procedure in the first year within the first year (34% by 10 years – as substantial numbers had developed symptoms during follow-up).

The median age of participants recruited to ACST-1 was 69 years, and 34% were women. The mean age of UK surviving participants is now 81 yrs. At the time of the last trial report (2010) median follow-up to 2008 was around 9 years (IQR 7-17 years) but with this study we would achieve an additional 10 years of follow-up.

For the short IQCODE questionnaire, the data linkage with UK National health records (n=1069) suggests the sample size for UK survivors is around 230, through all cause mortality. The IQCODE score is subjective, as it comes from an 'informant' questionnaire, but the questionnaire has been validated and should not bias between-group comparisons. We would expect some loss of response rate from survivors, but could reasonably expect this loss to be similar in both groups. Results from the IQCODE scores will add to and complement dementia data from data linkage with National electronic health records. Additionally the IQCODE will prove a useful measurement of current cognition in this previously randomised cohort.

9.2. Analysis of Outcome Measures

We will use the information obtained from the short IQCODE questionnaires to supplement the information gathered from National electronic health records.

Our analysis will compare participants in the treated (immediate CEA) group with those in the control group (deferred), as defined by the ACST-1 randomised allocation i.e. intention-to-treat analysis.

9.3. Planned analyses, tables and figures

The short IQCODE scores will supplement data obtained in the data linkage with electronic health records, chiefly through the detection of cognitive decline and the likelihood of dementia.

The main outcomes for the study (electronic data linkage and IQCODE follow-up) will be long-term rates of proven cognitive decline and proven dementia amongst those allocated immediate CEA plus medical therapy versus those allocated medical therapy alone. Cox proportional hazards will be used with Kaplan-Meier life-table analysis by "intention to treat". The analysis will compare dementia rates between treatment groups.

We will record IQCODE scores whether positive or negative for cognitive decline. The IQCODE score is calculated by adding the result for each question (Much improved = 1; A bit improved =2; Not much change

=3; A bit worse =4; Much worse =5) divided by the number of questions (16). The cut-off point for sensitivity and specificity for significant cognitive decline is ≥ 3.6 .

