This protocol is the final part of the research where we propose to complement the electronic data linkage already undertaken for dementia diagnosis with information from the short IQCODE questionnaire for UK survivors in ACST-1.

Our proposed research is therefore an important part of testing the hypothesis that, by undertaking CEA, cerebral embolization from carotid atheroma may be prevented, reducing later risk of dementia.

Patient numbers and the long follow-up in ASCT-1 may be sufficient to enable us to detect an effect of carotid intervention on dementia more reliably than any previous study. If a reduced risk of dementia is demonstrated in addition to the known reduction in subsequent stroke for participants who had endarterectomy, this would alter the perceived benefits and harms of surgery, and help future decision making for patients with carotid stenosis.

4. OBJECTIVES AND OUTCOME MEASURES FOR PHASE 2

Objectives	Outcome Measures	Timepoint(s) of evaluation of this outcome measure

Primary Objective: To provide current cognition information in surviving ACST-1 UK participants to add to the information on dementia provided through the completed data linkage part of the study.
 
The overall study may determine whether carotid endarterectomy reduces the long-term risk of dementia.
	
A cognitive impairment score to inform diagnosis of dementia and complementing data linkage with electronic health records
	
Single assessment by telephone via the short form of the Informant Questionnaire on Cognitive Decline in the Elderly (IQCODE). This is a validated screening assessment questionnaire for dementia by completed by a relative or friend (informant) determining changes in cognition from 10 years to the date of the assessment in the surviving participant. To be implemented Spring- 2019.

TABLE 1 Primary Objective and outcomes of the study: Phase 2

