6.2. Inclusion Criteria

Randomisation of participants in ACST-1 was performed via Clinical Trial Service Unit (CTSU), University of Oxford with participant details and data stored securely at CTSU.

Inclusion criteria:

1. ACST-1 participant
2. Resident in UK
3. Known to be alive in March 2019
4. Consented to take part and nominated a relative or friend to complete the IQCODE questionnaire

Exclusion Criteria:

None

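### Section 9.3 feeds a single, undated, survivor-only IQCODE screen into Cox and Kaplan-Meier outcomes, so the late absolute rates hinge on whichever event date is assigned

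*Protocol*

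**What the plan says.** Section 9.3 of the protocol sets the main outcomes: "The main outcomes for the study (electronic data linkage and IQCODE follow-up) will be long-term rates of proven cognitive decline and proven dementia", compared between the allocated arms. The method follows at once: "Cox proportional hazards will be used with Kaplan-Meier life-table analysis", by intention to treat. The section also says that IQCODE scores supplement the linked records, mainly by detecting cognitive decline, and gives a cut-off of 3.6 or more.

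Other sections describe what the IQCODE can supply:

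- **Timing.** Table 1 (Section 4) describes one telephone assessment, "To be implemented Spring- 2019".
- **Content.** The informant is asked about change, "determining changes in cognition from 10 years to the date of the assessment in the surviving participant" (Table 1).
- **Who.** Section 6.2 requires UK residence, consent, a nominated informant and "Known to be alive in March 2019". Section 7.1 puts this at about 230 of 1069 UK participants. The Synopsis gives the linked UK and Swedish cohort as 1601.
- **Capacity.** Under Section 7.3, any doubt about capacity stops the questionnaire.
- **Dates.** The only route to a diagnosis date in the survey is Section 7.3: if a relative happens to make contact, the coordinator may record one.

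The protocol states neither a time origin for the survival analysis nor the date that an IQCODE-positive result would carry.

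**The concern.** Cox and Kaplan-Meier methods in their usual form need each event to have a time, and need everyone at risk to be able to show the event when it happens. An IQCODE-only positive meets neither condition. Decline began at some unknown point before the call. It can be found only in people who lived to 2019, live in the UK, responded and were judged to have capacity. Someone with the same undiagnosed decline who died in 2012, or who was randomised in Sweden, stays event-free.

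Two things are at stake. First, Section 9.3 names long-term rates as the outcome, and Section 3 says the result could change the perceived balance of benefit and harm of surgery. Absolute late rates would therefore be read as findings. Second, Section 9.3 calls the outcomes *proven*, while Table 1 and Section 7.4 call the IQCODE a screening tool and Section 9.3 itself speaks of the likelihood of dementia. How a screening score contributes to a proven outcome is not settled.

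**Working it through.** **1. What the protocol's figures give.** No event rate, effect size or power is stated. The 230 is a count of survivors, so there is no sample-size calculation to reproduce.

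- Share of the linked cohort that can be screened: 230 / 1601 = 14.4%.
- Share of the UK cohort: 230 / 1069 = 21.5%.
- Swedish participants, none screened: 1601 − 1069 = 532.
- Linked participants with no possible IQCODE result: 1601 − 230 = 1371 (86%).
- Time from randomisation (1993–2003, Section 7.5) to spring 2019: from about 2019.3 − 2004.0 = 15.3 years to about 2019.3 − 1993.25 = 26.0 years.
- The 10-year window opens around 2009, about 5 to 16 years after randomisation.

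If positives are dated at the call, all of them fall at about 15 to 26 years. If they are back-dated, they become earlier events that only people still alive in 2019 can have.

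**2. How many events.** The response rate is not given. Assuming 40% to 100%, 92 to 230 people are screened. Assuming 10% to 30% positive, that is about 9 (92 × 0.10) to 69 (230 × 0.30) IQCODE events.

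**3. How much the date matters.** Illustrative simulation, 400 replicates.

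- From the protocol: 1601 participants, 1069 in the UK, entry 1993–2003 (taken as uniform), screen at 2019.3.
- Assumed: death hazard 4% a year rising 6% a year (giving about 218 UK survivors); dementia hazard 0.6% a year rising 9% a year; linkage sensitivity 50%; IQCODE sensitivity 80% and specificity 85%; response 60%; no treatment effect.

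Kaplan-Meier estimates, with about 29 IQCODE-only positives:

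| Version | 14 y | 20 y | 24 y |
|---|---|---|---|
| True onset | 15.6% | 28.5% | 40.0% |
| Linkage only | 7.8% | 14.2% | 19.8% |
| Plus IQCODE, dated at survey | 7.8% | 18.8% | 33.2% |
| Plus IQCODE, dated 5 years earlier | 9.5% | 19.5% | 25.9% |

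With the same people and the same positives, the dating choice alone moves the 24-year figure by 33.2 − 25.9 = 7.3 points. At 90% response the gap is 39.0 − 29.2 = 9.8 points.

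Under other assumed rates (dementia 1% a year, linkage sensitivity 60%, IQCODE accuracy and response as above), survey-dating leaves the 15-year estimate unchanged at 8.4%. It raises the 20-year estimate from 10.9% to 14.7% and the 25-year estimate from 13.1% to 28.6%, against a true 22.1%. Survey-dating thus ends below the truth in one setting and above it in the other.

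**4. The treatment comparison.** Cox hazard ratios from the main simulation:

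| Setting | Linkage only | Dated at survey | Dated 5 years earlier |
|---|---|---|---|
| No effect | 0.990 | 0.989 | 0.988 |
| True hazard ratio 0.80 | 0.810 | 0.831 | 0.833 |
| No effect on dementia, mortality hazard ratio 0.90 | 0.996 | 1.001 | 1.014 |

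The largest shift from linkage only is 0.833 − 0.810 = 0.023.

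**The case against.** Much of the opposing case stands.

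- **The text does not say that time runs from randomisation or that positives are dated at the call.** That is correct. Randomisation is the natural origin under intention to treat, but a dating rule could sit in an analysis plan that is not shown. The bracket in Section 9.3 may also describe the study rather than the outcome. Even so, the section makes the IQCODE a contributing source and fixes the method, and the mismatch between that method and a single undated screen exists whichever date is chosen.
- **A reader might infer that the treatment comparison is biased.** The documents do not support this. The survey date is common to both arms, Section 9.1 expects similar loss of response in each, and the hazard ratio barely moves.
- **A reader might infer that the late curves are simply an artefact.** That goes too far for dementia, because dated linked diagnoses also feed them. It comes closer for cognitive decline, since the protocol names no linked source for decline short of dementia.
- **Pooling can be nearer the truth than linkage alone.** It is at 20 and 24 years in the main simulation. In the second setting at 25 years, linkage is 22.1 − 13.1 = 9.0 points low and pooling 28.6 − 22.1 = 6.5 points high. Section 3 gives under-ascertainment in linked records as the reason for Phase 2. Making linkage the only main event would therefore be a debatable choice, and it is not asked for here.
- **The word *proven* could mean that more than a screen result is required.** It could. But then the plan does not say what turns a score of 3.6 or more into a proven case, so the wording needs settling either way.

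**Conclusion.** The point holds as a mismatch between the stated method and the data. An interval-censored finding, available for at most about 14% of the linked cohort and only in survivors, is to enter an analysis that in its ordinary form treats it as an exactly timed event. The consequence is confined mainly to late absolute rates and curve shape, above all for cognitive decline. The 24-year estimate ranged from 25.9% to 33.2% on the dating choice alone, against 19.8% for linkage only. These sizes rest on assumed death, dementia, accuracy and response rates and are illustrative; the mechanism does not depend on them. Few participants can reach the longest times, so the effect is smaller at 20 years and, with survey-dating, absent before about 15 years.

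The hazard ratio shifts by about 0.02, provided that survival and response are similar by arm. The protocol expects this for response but cannot guarantee it. This should be fixed, but it does not invalidate the trial's main comparison.

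**What to change.** Reword Section 9.3 on three points.

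1. Report the Cox and Kaplan-Meier analysis of dated, linked dementia in all 1601 participants on its own, with the time origin stated.
2. Report the IQCODE separately as a 2019 comparison by allocated arm in UK survivors: the proportion scoring 3.6 or more, and the mean score. State that it is conditional on survival and response. Label it *IQCODE-positive decline over the last 10 years* and do not call it *proven*.
3. Where linkage and IQCODE are combined to address under-ascertainment, treat IQCODE-only positives as interval-censored, with the interval stated (the 10 years before the call is the natural candidate), not as events on one date. Show results with and without the IQCODE, because interval-censoring does not cure the restriction to survivors.

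The cost is some rewording and a little more analysis. The linkage-only analysis has fewer events than a pooled one. No new data are needed.

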10. DATA MANAGEMENT

10.1. Access to Data

Direct access will be granted to authorised representatives from the Sponsor, appropriate regulatory bodies and host institution for monitoring and/or audit of the study to ensure compliance with regulations.

10.2. Data Recording, Record Keeping and Data Security

CTSU researchers are experienced in handling confidential and participant sensitive data and have appropriate training in information governance.

The CTSU servers are protected against unauthorised external access by an appropriate strength firewall. Access to patient identifiable information is protected by the appropriate authentication procedures (user IDs and passwords.) Authentication is only given to personnel with a need to access the required data. Only personnel involved in the long-term follow-up study for ACST-1 study (processing and analysing data) will have access to this data. CTSU has a Corporate Level Security Policy that has been fully adopted by management and will apply fully to the long-term follow-up study. The data protection Registration Number is Z575783X.

Security Arrangements for the storage of data

CTSU is a secure building with access limited to employees and authorised visitors. The study servers are located in a climate controlled secure enclosure to which only system support staff have access. Offices will be routinely locked when not in use. Password protected screen savers will be routinely employed. IT equipment and media will be used within the manufacturer's environmental specifications. The data will be stored on secure servers at the Clinical Trial Service Unit (CTSU), University of Oxford. CTSU computers are in a secure building protected by a firewall. All CTSU employees agree to maintain confidentiality at all times as part of their employment contract with the University of Oxford and all University departments will have the similar clauses in their contracts. Access to study data will require a username and password combination and will be audited. Study staff only have access to data appropriate to their role. CTSU is subject to successful audit of computer security and similar audits.

11. QUALITY ASSURANCE PROCEDURES

The study may be monitored, or audited in accordance with the current approved protocol, GCP, relevant regulations and standard operating procedures.

12. ETHICAL AND REGULATORY CONSIDERATIONS

12.1. Declaration of Helsinki

The Investigator will ensure that this study is conducted in accordance with the principles of the Declaration of Helsinki.

12.2. Guidelines for Good Clinical Practice

The Chief Investigator will ensure that this study is conducted in accordance with relevant regulations and with Good Clinical Practice.

12.3. Approvals

The protocol, consent, participant information sheet, and proposed IQCODE questionnaire will be submitted to an appropriate HRA Research Ethics Committee (REC) the Confidentiality Advisory Group (CAG) and host institution for written approval.

The Chief Investigator will submit and, where necessary, obtain approval from the above for all substantial amendments to the original approved documents.

12.4. Reporting

The Chief Investigator shall submit once a year or more frequently on request, an annual progress report to the REC Committee, CAG, funder and Sponsor. In addition, an end of study notification and final report will be submitted to the same parties.

12.5. Participant Confidentiality

All information collected will be kept strictly confidential. The names of the interviewed participants and previous ACST-1 participants will only be available to the research staff via their unique study number. All study documentation including Consent forms will be kept in locked filing cabinets in a secure room and will be destroyed after 25 years. Files containing electronic data will be password protected and stored on a secure network and these files will be destroyed after 25 years. The Chief Investigator and research staff will be allowed access to the secure network and individuals will not be identified in any publications.

12.6. Other Ethical Considerations

Purpose and design

The prevention of dementia is a current public health priority. This research aims to address the question whether or not carotid endarterectomy in middle age may lead to a reduction in risk of dementia or stroke in the longer term. This question is worth answering. If we demonstrate that treatment that lower the risk of stroke also lower the risk of dementia, then this will increase the benefit of these treatments. In the long-term, this may lead to a reduction in the numbers of people who develop dementia over their lifetime and in the short term, it could help patients and their doctors make better decisions about their treatment.

This information is difficult to obtain. It might come from: (i) very large, expensive long-term randomised trials but these are complex (and would require many years to undertake); (ii) from observational studies comparing risk of dementia in participants offered endarterectomy with those who are not; however a problem with 'confounding by indication' would then exist, as important differences between people who do and do not take medication, or have interventions, probably influence their risk of stroke, which is the current indication for this surgery; or (iii) the very long-term follow-up of older randomised controlled trials, with large numbers of patient-years data, as we propose.

CTSU has, with patient consent securely held participant information from the original ACST-1 trial.

Implementing the short IQCODE screening questionnaire for UK participants will reliably complement the information on cognitive decline and dementia diagnosis already provided from the National electronic health records.

Risks, burdens and benefits

There are no direct benefits to the participants taking part in this study.

The study does not involve any additional physical risk to the participants and is one single questionnaire only. We are aware of the sensitive nature of implementing the IQCODE questionnaire in an elderly population but in our experience the questionnaire is acceptable to participants and informants and therefore we do not expect any significant risks associated with it.

13. FINANCE AND INSURANCE

13.1. Funding

Supported by an Alzheimer's Society project grant, Oxford Biomedical Research Centre (OBRC) and CTSU core funding.

13.2. Insurance

The University of Oxford maintains Public Liability and Professional Liability insurance which will operate in this respect.

[figure not shown]
14. PUBLICATION POLICY

The Investigators will be involved in reviewing drafts of the manuscripts, abstracts, press releases and any other publications arising from the study. Authors will also acknowledge the original funders of the ACST-1 trial. Authorship will be determined in accordance with the ICMJE guidelines and will be on behalf of the ACST-1 collaborative group. Other contributors will be acknowledged, particularly ACST-1 participants.

APPENDIX A: Flow Chart for use of Short IQCODE Questionnaire

APPENDIX B: AMENDMENT HISTORY

Amendment No.	Protocol Version No.	Date issued	Author(s) of changes	Details of Changes made
1	V2.0	18 February 2019	UK Collaborators on project (listed on page 1 of the protocol)	Changes to methodology from recommendations following Ethics and CAG review

List details of all protocol amendments here whenever a new version of the protocol is produced.
